5.2. Exclusion Criteria

Each subject/patient must not meet any of the following exclusion criteria to be eligible for enrollment in the study.

5.2.1. Exclusion Criteria for Parts A and B

1. Any uncontrolled or serious disease, or any medical or surgical condition (with the exception of PH1 for patients in Part B) that may either interfere with participation in the clinical study, and/or put the subject significant risk (according to the Investigator's judgment) if he/she participates in the clinical study
2. An underlying known disease or surgical or medical condition (with the exception of PH1 for patients in Part B) that in the opinion of the investigator might interfere with the interpretation of the clinical study results
3. Triplicate 12-lead ECG with clinically significant abnormalities
4. Active serious mental illness or psychiatric disorder including, but not limited to, schizophrenia, bipolar disorder, or severe depression requiring concurrent pharmacologic intervention
5. Clinically significant illness (with the exception of PH1 for patients in Part B) within 7 days before the first dose of study drug
6. Male and female subjects/patients aged 18 to 64 years (or age of legal consent, whichever is older), systolic blood pressure >140 mm Hg and/or a diastolic blood pressure >90 mmHg after 10 minutes of rest at screening
7. Abnormal for AST/ALT and any other clinical safety laboratory result considered clinically significant and unacceptable by the Investigator at screening or Day -1

8. Received an investigational agent within 90 days or 5 half-lives of the first dose of ALN-GO1 study drug, whichever is longer, or in the active follow-up phase of another clinical trial involving interventional treatment
9. Clinical laboratory evidence or a clinical diagnosis of viral hepatitis or human immunodeficiency virus (HIV) infection
10. Consume more than 14 (female) or 21 (male) units of alcohol per week (1 unit=1 glass of wine (125 mL), 1 measure of spirits or ½ pint of beer (subjects/patients above the age of legal consent). Alcohol abuse is defined as regular weekly intake of more than 21 units for males and 14 units for females (using alcohol tracker at <http://www.nhs.uk/Tools/Pages/NHSAcoholtracker.aspx>).
11. History or clinical evidence of drug abuse, within the 12 months before screening. Drug abuse is defined as compulsive, repetitive and/or chronic use of drugs or other substances with or without problems related to their use and/or where stopping or a reduction in dose will lead to withdrawal symptoms (subjects/patients above the age of legal consent).
12. Positive for drugs of abuse at screening (subjects/patients above the age of legal consent)
13. Heavy smokers and users of nicotine (defined as the equivalent of ≥10 cigarettes per day).
14. Known history of allergic reaction to an oligonucleotide or GalNAc
15. History of intolerance to SC injection or relevant abdominal scarring (eg, surgical, burns)
16. Legal incapacity or limited legal capacity at screening of patient, parent, or legal guardian
17. Any conditions which, in the opinion of the Investigator would make the subject/patient unsuitable for enrollment or could interfere with the subject's/patient's participation in, or completion of, the study.
18. Donation of more than 500 mL of blood for adults (>18 years of age) within 90 days before the first dose of study drug (it is expected that children [6 to 18 years of age] will not have donated blood).
19. Women who are pregnant or breastfeeding

5.2.2. Additional Exclusion Criteria for Part B

20. Clinical evidence of systemic oxalosis, including but not limited to, myocardial dysfunction, bone marrow, bone, or eye infiltration with oxalate as determined by the Investigator
21. For patients <18 years old, diastolic and/or systolic blood pressure equal to or greater than the 95th percentile for age, gender, and height (see Appendix 11.4 Table 14 and Table 15) after 10 minutes of rest at screening.
22. Echocardiography (Echo) assessment of abnormal left ventricular systolic function, defined as left ventricular ejection fraction <55% at screening
23. Troponin I greater than the upper limit of normal (ULN) at screening (abnormal results should be repeated)

5.3. Removal from Therapy or Assessment

Subjects/Patients are free to discontinue treatment or withdraw from the study at any time and for any reason, without penalty to their continuing medical care. Any discontinuation of treatment or withdrawal from the study must be fully documented in the electronic case report form (eCRF), and should be followed up by the Investigator. The Investigator may withdraw a subject/patient at any time if this is considered to be in the subject's/patient's best interest.

Discontinuation of study drug and withdrawal from the study are described in Section 5.3.1 and Section 5.3.2, respectively.

5.3.1. Discontinuation of Study Drug

The Investigator or designee may discontinue dosing in a subject/patient if the subject/patient:

- Is in violation of the protocol
- Experiences a serious or intolerable AE
- Requires a prohibited medication
- Becomes pregnant
- Is found to be noncompliant with the protocol-requirements in a manner that is considered by the Investigator to compromise patient safety and/or the integrity of the study

The Investigator will confer with the Sponsor, or Medical Monitor, before discontinuing dosing. Subjects/Patients who are pregnant will be discontinued from dosing immediately (see Section 7.5.7.6 for reporting and follow-up of pregnancy). Subjects/patients who discontinue study drug may be replaced (see Section 5.3.3). Subjects/patients who discontinue study drug dosing for any reason will be encouraged to complete the remaining assessments through the remaining scheduled study visits so that their experience is captured in the study analyses. Subjects/Patients who discontinue study drug but who agree to attend the remaining scheduled study visits will not be considered withdrawn from study. Such subjects/patients may receive local standard of care treatment for their disease, as applicable.

5.3.2. Withdrawal From Study

A subject/patient may withdraw from the study at any time. However, study integrity and interpretation is optimal if all randomized patients continue study assessments and follow-up. Subjects/Patients considering withdrawing from the study should be informed that they can alternatively discontinue study treatment and complete the remaining scheduled study visits or agree to alternative follow-up processes (as described in Section 5.3.1).

If a subject/patient still chooses to withdraw consent/assent, every effort should be made to conduct the assessments performed at the EOT visit. When a subject/patient withdraws from the study, the primary reason for withdrawal must be recorded in the appropriate section of the eCRF and all efforts will be made to complete and report the observations as thoroughly as possible. If a subject/patient withdraws due to a serious adverse event (SAE), the SAE should be followed as described in Section 7.5.7.

5.3.3. Replacement of Subjects or Patients

Replacement subjects/patients may be enrolled to ensure that the minimum data requirements for SRC dose escalation decisions and study progression are met, as described in Section 4.6 and Section 4.7. Subjects/patients who are discontinued from treatment for reasons other than experiencing an AE may be replaced following discussion between the Sponsor and Investigator.

The replacement subject/patient will be assigned a unique study identification number and will receive the same study drug assignment and dose level as the subject/patient who is being replaced.

6. TREATMENTS

6.1. Treatments Administered

The treatments administered in this study are ALN-GO1 and placebo. ALN-GO1 is a synthetic, double-stranded small interfering RNA oligonucleotide directed against hydroxyacid oxidase 1 mRNA that is covalently linked to a ligand containing 3 N-acetylgalactosamine residues.

Study drug supplied for this study must not be used for any purpose other than the present study and must not be administered to any person not enrolled in the study. Study drug that has been dispensed to a subject/patient and returned unused must not be re-dispensed to a different subject/patient.

6.2. Investigational Study Drug

Detailed information describing the preparation, administration, and storage of ALN-GO1 is provided in the Pharmacy Manual.

6.2.1. Description

ALN-GO1 Solution for Injection (SC use) is a clear, colorless to pale yellow solution essentially free of particulates. ALN-GO1 will be supplied by the Sponsor as a sterile solution for SC injection at a targeted concentration of 200 mg/mL. Placebo will be supplied by the clinical study center as a sterile, preservative-free normal saline 0.9% solution for SC injection.

6.2.2. Dose and Administration

Dose cohorts for this study are described in Section 4.7.1 (Part A) and Section 4.7.2 (Part B). Subjects/patients will be administered study drug by SC injection(s). Study drug will be administered by qualified clinical study center staff under the supervision of the Investigator, or designee, and the injection site will be marked and mapped for later observation. The preferred site of injection is the abdomen. Optional additional sites are the upper arms and thighs. If a local reaction around the injection site occurs, photographs may be obtained. Detailed instructions for study drug administration are in the Pharmacy Manual.

6.2.3. Dose Modifications

The dose modifications permitted in this study are described in Section 4.7.3.

6.2.4. Preparation, Handling, and Storage

Study drug may be dispensed only by the Investigator, by a staff member specifically authorized by the Investigator, or by pharmacy staff, as appropriate.

Each clinical study center will be responsible for assembly and labeling of injection syringe(s) according to procedures detailed in the Pharmacy Manual. The pharmacy staff will prepare the study drug using an aseptic technique. The amount (in mg) of study drug to be administered will be determined based on the assigned dose level for the cohort and the Day -1 body weight for healthy subjects and patients with PH1. On dosing days, the pharmacist, or designee, will withdraw the required amount of study drug into 1 or more syringes to be administered to the subject/patient on that day. The procedure for preparing study drug and the volume to be loaded into each syringe is provided in the Pharmacy Manual.

No special procedures for the safe handling of ALN-GO1 are required. Study drug will be stored upright and refrigerated at approximately 2 to 8°C protected from light in the storage area of the clinical study center pharmacy, in a secure, temperature-controlled, locked environment with restricted access. Any deviation from the recommended storage conditions should be reported to the Sponsor and use of the study drug halted until authorization for its continued use has been provided by the Sponsor or designee. Additional storage details are provided in the Pharmacy Manual.

A Sponsor representative or designee will be permitted, upon request, to audit the supplies, storage, dispensing procedures, and records.

6.2.5. Packaging and Labeling

ALN-GO1 (solution for SC injection) is packaged in 2-mL glass vials with a fill volume of no less than 0.55 mL to allow for complete withdrawal of 0.5 mL of drug product at the pharmacy. The container closure system consists of a Type I glass vial, a Teflon-faced 13-mm stopper, and a flip-off aluminum seal.

6.2.6. Accountability

The Investigator or designee will maintain accurate records of receipt and the condition of the study drug supplied for this study, including dates of receipt. In addition, accurate records will be kept of when and how much study drug is dispensed and administered to each patient in the study. Any reasons for departure from the protocol dispensing regimen must also be recorded.

At the completion of the study, there will be a final reconciliation of all study drugs.

Further instructions about drug accountability are detailed in the Pharmacy Manual.

6.3. Concomitant Medications

All concomitant medications must be recorded in the eCRF. Concomitant medications will be coded using the WHO Drug Dictionary.

Any concomitant medication that is required for the patient's welfare may be administered by the Investigator. However, it is the responsibility of the Investigator to ensure that details regarding the medication are recorded on the eCRF.

6.3.1. Permitted Concomitant Medications

For Part A and Part B, the following medications/treatments are permitted:

- hormone replacement therapy
- oral contraceptives, injectable progesterone, and subdermal implants are permitted for contraception
- acetaminophen (maximum 2 g daily) for treatment of AEs
- at the discretion of the Investigator, prescription or nonprescription medications may be permitted when necessary to treat an AE; before the subject uses any prescription or nonprescription medications, the Investigator or delegate must be consulted and justify their use

For Part B, the following medication/treatment is also permitted:

- Vitamin B6 (pyridoxine): If taking vitamin B6, must have been on stable regimen for at least 90 days before study entry, and willing to remain on this stable regimen for the study duration.
- Sodium or potassium citrate

6.3.2. Prohibited Concomitant Medications

For Part A, the following medications/treatments are not permitted:

- Any OTC medications, except routine vitamins from 7 days before the first dose of study drug, unless considered not clinically relevant by the Investigator and Sponsor
- Prescription medications not specified in Section 6.3.1 from 14 days or 5 half-lives (whichever is longer) before the first dose of study drug.

For Part B, there are no prohibited medications; however, all concomitant medications must be reviewed by the Investigator.

6.4. Contraceptive Requirements

Women of child-bearing potential (WOCBP) must be willing to use a highly effective method of contraception 14 days before first dose, and throughout study participation until the completion of the follow-up periods. Highly effective methods of birth control result in a low failure rate (ie, less than 1% per year). Birth control methods, which may be considered as highly effective, include:

- Established use of oral (except low-dose gestagens [eg, lynestrenol and norethisterone]), implantable, injectable, or transdermal hormonal methods of conception
- Placement of an intrauterine device
- Placement of an intrauterine hormone-releasing system
- Bilateral tubal occlusion

- Surgical sterilization of male partner (with the appropriate post-vasectomy documentation of the absence of sperm in the ejaculate; for female patients on the study, the vasectomized male partner should be the sole partner for that patient);
- True sexual abstinence, when in line with the preferred and usual lifestyle of the patient (and for adolescents who are not sexually active). Periodic abstinence (eg, calendar, ovulation, symptothermal, post-ovulation methods) and withdrawal are not acceptable methods of contraception. Abstinent subjects have to agree to use 1 of the abovementioned contraceptive methods, if they start sexual relationships during the study until the completion of the follow-up periods.

WOCBP includes any female patient who has experienced menarche and who is not postmenopausal or permanently sterilized (eg, bilateral tubal occlusion, hysterectomy, or bilateral salpingectomy). Postmenopausal state is defined as no menses for 12 months without an alternative medical cause, confirmed by follicle stimulating hormone (FSH) level within the postmenopausal range.

No male contraception is considered to be required.

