Review/record AEs ^y			X																		
Prior and concomitant medications		X																			

Abbreviations: ADA=antidrug antibodies; AE=adverse event; BMI=body mass index; D=day; ECG=electrocardiogram; Echo=echocardiography; eGFR=estimated glomerular filtration rate; EOT=end of treatment; FSH=follicle-stimulating hormone; ICF=informed consent form; LFT=liver function test; PD=pharmacodynamics; PK=pharmacokinetic; Q=every; SC=subcutaneous.

Notes:

- When scheduled at the same time points, the assessments of vital signs and 12-lead ECGs must be performed first, before the physical examinations, blood sample collections, and urine collections.
- Assessments should be performed predose, where applicable, unless otherwise noted.

- Grey columns indicate the study day when the 24-hour urine collection for PD analysis should begin. Patients may be admitted to the clinical study center to complete the 24-hour urine collections.
 - a. Patients will be invited to participate in an open-label extension study once they complete the postdose follow-up period on Study Day 141. For patients who do not enroll in the open-label extension study, safety and PD follow-up will continue until plasma glycolate is <20% above baseline or \leq the ULN AND 24-hour urinary oxalate is >80% of baseline, or until the SRC makes a decision per investigator request to discontinue follow-up on a case-by-case basis. The decision cannot be made until after completion of the postdose follow-up period (84 days after last dose).
 - b. Patients initially randomized to placebo may continue in the study receiving administration of open-label ALN-GO1 according to the Schedule of Assessments (Table 3). Patients will be unblinded on or after Day 78.
 - c. Complete medical history (including documentation or confirmation of PH1) will be obtained at screening and any changes will be updated on Day -1. AEs occurring after signing of the ICF and before study drug administration will be captured as medical history.
 - d. See Section 7.5.3 for assessments to be performed during a full physical examination or symptom-directed physical examination.
 - e. During screening and at EOT, height will be measured for all patients; thereafter, height will only be measured for patients <18 years of age. Additionally, for patients <18 years of age, at each time point, height will be measured in centimeters, and in triplicate, to facilitate calculation of eGFR using the Schwartz Bedside Formula.

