	84	85	86	87	99	112	113	127	140	141/EOT ^b	142	143	168	169	196	197	224	225	253; then, Q28D
Visit Window (D)					±2		±4	±4						±4		±4		±4	±4
Blood and urine samples for exploratory ██████████		X ^r					X							X		X			
Blood sample for pyridoxine (vitamin B6) levels ^s		X					X							X		X		X	
Blood samples for ADA analysis		X					X							X				X	X ^t
Review/record AEs	X																		
Concomitant medications	X																		

Abbreviations: ADA=antidrug antibodies; AE=adverse event; BMI=body mass index; D=day(s); ECG=electrocardiogram; Echo=echocardiography; eGFR=estimated glomerular filtration rate; EOT=end of treatment; PD=pharmacodynamics; PK=pharmacokinetic; Q=every; SC=subcutaneous.

Notes:

- When scheduled at the same time points, the assessments of vital signs and 12-lead ECGs must be performed first, before the physical examinations, blood sample collections, and urine collections.
- Assessments should be performed predose, where applicable, and unless otherwise noted.
- Grey columns indicate the study day when the 24-hour urine collection for PD analysis should begin. Patients may be admitted to the clinical study center to complete the 24-hour urine collections.
 - a. Patients will be invited to participate in an open-label extension study once they complete the postdose follow-up period on Study Day 225. For patients who do not enroll in the open-label extension study, safety and PD follow-up will continue until plasma glycolate is <20% above baseline or ≤ the ULN AND 24-hour urinary oxalate is >80% of baseline, or until the SRC makes a decision per investigator request to discontinue follow-up on a case-by-case basis. The decision cannot be made until after completion of the postdose follow-up (84 days after last dose).
 - b. If a patient chooses to withdraw consent, every effort should be made to conduct the assessments performed at the EOT visit.
 - c. See Section 7.5.3 for assessments to be performed during a full physical examination or symptom-directed physical examination.
 - d. On Day 85 and at EOT, height will be measured for all patients; thereafter, height will only be measured for patients <18 years of age. Additionally, for patients <18 years of age, at each time point, height will be measured in centimeters, and in triplicate, to facilitate calculation of eGFR using the Schwartz Bedside Formula.
 - e. The Day 57 body weight will be used for calculation of the ALN-GO1 dose to be administered during this portion of the study.

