After the dosing period, patients will return to the clinical study center for continued safety, tolerability, PK, and PD monitoring for at least 12 weeks (84 days) following the last dose of study drug. Following completion of the 12-week postdose follow-up period, patients will be invited to participate in an open-label extension study.

For patients who do not enroll in the open-label extension study, safety and PD follow up will continue until 24-hour urinary oxalate is $>80\%$ of baseline, and plasma glycolate is $<20\%$ above baseline or \leq the ULN. If an investigator wishes to discontinue follow up after completion of the postdose follow-up period and prior to oxalate and glycolate recovery, the SRC must agree based upon consideration of emerging data on the safety of ALN-GO1 knockdown and the individual patient's safety and PD data.

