4.2. Duration of Treatment and Overall Duration of Study

The duration of treatment is as follows:

- Part A: The estimated total time on study, inclusive of screening, for each subject is up to 405 days. The duration of treatment is a single dose.
- Part B: For all patients, the duration of screening is up to 45 days and the minimum duration of postdose follow-up is 84 days. The duration of treatment and estimated total time on study, inclusive of screening, for each patient is as follows:
 - For patients dosed monthly: The duration of treatment for patients initially randomized to receive active study drug is 57 days. The estimated total time on study is up to 462 days. Additionally, the duration of treatment for patients initially randomized to receive placebo is 141 days. The estimated total time on study for each patient initially randomized to receive placebo, then active study drug, is up to 546 days.
 - For patients dosed quarterly: The duration of treatment is 85 days for patients randomized to placebo and active study drug. The estimated total time on study is up to 490 days.

The overall duration of the study is estimated to be 4 years, including enrollment.

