4.6. Safety Review Committee

A SRC will perform ongoing reviews of safety, tolerability, and available study data collected in all study parts (Parts A and B) with the primary purpose of protecting the safety of subjects/patients participating in this clinical study. The SRC will undertake safety data review before initiation of dosing in a new cohort in Part A and Part B, and before initiation of dosing in Part B. After initiation of dosing in Part B, safety reviews will be conducted in accordance with the SRC charter at a minimum of every 3 months for the duration of the study. Part A and Part B of the study will incorporate adaptive study design features, which will allow for the continuing modification of dosing options and/or regimen as new data emerge, and in accordance with recommendations of the SRC (Table 9). Protocol-defined stopping rules will be used as criteria for stopping cohorts (Table 6) or individual patients (Table 7). Additionally, the SRC may recommend discontinuation of the study at its discretion. The investigator may also request that the SRC determine on a case-by-case basis whether study follow-up will be discontinued in patients in Part B who do not enroll in the open-label extension study who have completed the postdose-follow up period, but have not yet met the recovery criteria for plasma glycolate and urinary oxalate specified in Section 4.1.2. The decision will be informed by emerging data on the safety of ALN-GO1 knockdown and the individual patient's safety and PD data.

The SRC will be comprised of the Sponsor Medical Monitor, a Medical Monitor from the CRO, the Principal Investigator from the clinical study center conducting Part A of the study, an independent pediatrician experienced in clinical investigation who is not a study Investigator, and 3 Investigators at the clinical study sites who will be selected by the Sponsor.

The SRC will be governed by a charter that will be signed prior to enrollment of the first subject.

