5.1.1. Inclusion Criteria for Parts A and B

1. Male and female subjects aged 18 to 64 years (or age of legal consent, whichever is older), inclusive (Part A) and 6 to 64 years, inclusive (Part B).
2. Women of child-bearing potential must have a negative pregnancy test, cannot be breast feeding, and must be willing to use a highly effective method of contraception 14 days before first dose, throughout study participation until the completion of the follow-up periods (see [Section 6.4](#)).

3. Willing to comply with protocol-required visit schedule and visit requirements; and able to provide written informed consent and assent in the case of patients under the age of legal consent.

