7.5.6.2. Pregnancy Testing

A pregnancy test will be performed for WOCBP only. A serum pregnancy test will be performed at Screening or after the onset of menarche if the patient was not of childbearing potential at screening, and urine pregnancy tests will be performed thereafter per the Schedule of Assessments and any time pregnancy is suspected. The results of the pregnancy test must be known before study drug administration. Women who are pregnant are not eligible for study participation. Any woman with a positive pregnancy test during the study will be discontinued from study drug, but will continue to be followed for safety. Women determined to be pregnant while on study will be followed until the pregnancy outcome is known (see Section 7.5.7.6 for follow-up instructions).

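### In Part B, an SRC-agreed early stop ends required contraception before oxalate and glycolate recover, and the SRC need not consider contraception when agreeing to it

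*Protocol*

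**What the plan says.** **Contraception.** Inclusion criterion 2 (Protocol Section 5.1.1) requires highly effective contraception from "14 days before first dose, throughout study participation until the completion of the follow-up periods". Section 6.4 sets the same end: "throughout study participation until the completion of the follow-up periods". Neither names a number of days, a date or a pharmacodynamic (PD) threshold.

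**Follow-up in Part B.** Under Section 4.1.2, a patient who does not enter the extension is followed until 24-hour urinary oxalate exceeds 80% of baseline and plasma glycolate is less than 20% above baseline or no higher than the upper limit of normal. The same section allows an investigator to ask to "discontinue follow up after completion of the postdose follow-up period and prior to oxalate and glycolate recovery", provided the SRC agrees. Footnote a of Tables 2 to 4 lists that SRC decision as an alternative end of follow-up, and the Figure 1 footnote does the same. The timing limit in Tables 2 and 4 reads: "The decision cannot be made until after completion of the postdose follow-up period (84 days after last dose"). Table 3 has the same limit.

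**Basis for the SRC decision.** Section 4.6 says "The decision will be informed by emerging data on the safety of ALN-GO1 knockdown", together with the patient's own safety and PD data. Section 4.1.2 gives the same basis.

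**Pregnancy testing and reporting.** Section 7.5.6.2 provides for a serum test at screening (or after menarche), after which "urine pregnancy tests will be performed thereafter per the Schedule of Assessments and any time pregnancy is suspected". In Tables 2 to 4 the late tests belong to the 28-day follow-up visits. Section 7.5.7.6 requires reporting of pregnancies that arise in the course of the study, and Section 7.5.6.2 follows the outcome of pregnancies found while the woman is on study.

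**Risk statement.** Section 1.5 lists embryofetal toxicity among the potential risks, says there are no data on use in pregnancy, and names contraception as specified in the protocol as one of the means of limiting the risk.

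**The concern.** An end of contraception tied to follow-up protects the patient through PD recovery only if follow-up itself runs to recovery. The SRC-agreed stop breaks that link. It applies, by its own terms, to a patient who has not yet recovered, and it ends the contraception requirement and the scheduled pregnancy tests in the same act. The decision criteria mention neither childbearing potential nor contraception, so the requirement can lapse without anyone having considered whether it should.

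At stake is a pregnancy conceived while glycolate oxidase may still be suppressed, with a drug for which the protocol reports no pregnancy experience. A fetal outcome cannot be undone, so the gap deserves a sentence even if it is rarely reached.

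**Working it through.** No statistical figure is involved. The check sets the provisions side by side and then sizes the interval.

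**1. Who is affected.** A Part B woman of childbearing potential who does not enter the extension, whose investigator asks to stop, whose SRC agrees, and who has not met both recovery criteria. Part A (Section 4.1.1) has no SRC release. Withdrawal of consent (Section 5.3.2) is a separate matter.

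**2. When her contraception requirement ends.** Sections 5.1.1 and 6.4 end it at completion of the follow-up periods. Footnote a ends follow-up at recovery or at the SRC decision, whichever applies. It follows that the requirement ends at the SRC-agreed stop.

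**3. Her state at that moment.** Recovery needs both the oxalate and the glycolate criterion. A stop before recovery means that at least one is unmet.

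**4. What the SRC must weigh.** Emerging data on the safety of knockdown, and her own safety and PD data. It may consider embryofetal risk under those headings, but no text requires it to, or requires an end date for contraception.

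**5. What continues after exit.** No scheduled visit and no scheduled pregnancy test. If the course of the study in Section 7.5.7.6 is read with Section 9.1.4 (last patient last visit), reporting could outlast her exit, but no planned contact would bring a pregnancy to light.

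**6. Earliest stop.** Last dose day + 84:
- Monthly, active: 57 + 84 = Day 141
- Monthly, placebo then active: 141 + 84 = Day 225
- Quarterly: 85 + 84 = Day 169

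These match the ends of the postdose follow-up period in footnote a of Tables 2, 3 and 4.

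**7. How long follow-up might otherwise run.** Section 4.2 gives estimated times on study; for monthly active patients, "The estimated total time on study is up to 462 days". Removing 45 days of screening and the day of the last dose:
- Monthly, active: 462 − 45 − 57 = 360 days after the last dose
- Monthly, placebo then active: 546 − 45 − 141 = 360
- Quarterly: 490 − 45 − 85 = 360

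The difference from the earliest stop is 360 − 84 = 276 days. The nominal 28-day visits in that interval are:
- Monthly, active, Days 169 to 393: (393 − 169)/28 + 1 = 9
- Monthly, placebo then active, Days 253 to 477: (477 − 253)/28 + 1 = 9
- Quarterly, Days 197 to 421: (421 − 197)/28 + 1 = 9

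A tenth fits in each schedule if the 4-day visit window is used: nominal Days 421, 505 and 449 can fall on Days 417, 501 and 445.

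These figures describe monitoring that may end early. They rest on planning estimates, because follow-up to recovery has no cap and the documents give no time-to-recovery data for Part B.

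**The case against.** The best defence is that the text is consistent and already guarded. Footnote a makes the SRC decision a defined end of follow-up, contraception is required for at least 84 days after the last dose, and the stop is not automatic. The investigator must ask, and the SRC, whose primary purpose is participant safety, must agree after looking at the very PD measures that define recovery. It can refuse, which keeps the patient under contraception and 28-day testing. No current section makes PD recovery a threshold for contraception. That link comes partly from the rationale for Amendment 2, which calls the relationship of the nonclinical findings to the test article uncertain. The rationale for Amendment 5 says no safety concern of knockdown had been identified.

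Most of this stands, and it disposes of one stronger reading. A reader might infer that after an SRC stop the obligation has no end date, or that the site has no protocol basis for telling the patient when she may stop. Footnote a does not support that: the SRC decision ends follow-up, and contraception ends with it.

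The defence does not meet the remaining point. On that same natural reading, the rule releases an unrecovered patient from contraception through a decision that need not consider it. The power to refuse is all or nothing: the SRC has no stated way to agree to the stop while keeping contraception in place. And current Section 1.5, quite apart from any amendment log, treats embryofetal toxicity as a potential risk to be limited by contraception.

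It is also fair to say that extended reporting would be passive, since no contact after exit is added. That is why the change needs counselling at exit.

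**Conclusion.** The concern holds in a limited form. For a Part B woman of childbearing potential outside the extension, an SRC-agreed stop ends required contraception and scheduled pregnancy testing as early as 84 days after the last dose and before recovery, and the SRC is not required to consider contraception.

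The number affected is small, possibly zero. Part B has up to 24 patients, including males and children, and all the conditions in step 1 must coincide. This is a cheap patient-safety improvement, not a demonstrated hazard.

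A reader might take the 276 days, or the 9 to 10 tests, as the benefit of the fix. They are not: they size the monitoring that could end early, and the fix restores none of it.

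The conclusion assumes that footnote a governs when follow-up is complete. The SRC charter, Investigator's Brochure and consent form were not available and may already cover the point. The SAP does not address how long contraception lasts or pregnancy reporting, so no analysis is affected.

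**What to change.** - **Sections 4.1.2 and 4.6:** where follow-up is stopped before the recovery criteria are met in a woman of childbearing potential, require the decision to record a contraception end date set by the SRC, and require the site to counsel her at exit.
- **Sections 5.1.1 and 6.4:** run contraception to completion of follow-up or, after a stop before recovery, to that date.
- **Section 7.5.7.6:** extend pregnancy reporting to the same date.

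The cost is about one sentence in each of the three places, one extra item per early-stop decision, and possibly longer contraception for a few patients. The SRC would have to choose the date without Part B time-to-recovery data in these documents, but it must already review the patient's own safety and PD data when deciding on the stop.
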